### 2.3.3 Medical History

Relevant medical history/current medical conditions will be summarized by primary system organ class, preferred term, and treatment group. Frequencies and percentages of patients in the FAS in each treatment group will be presented.

## 2.4 Treatments

The following descriptive analyses will be performed on the SAF by treatment group and total, unless otherwise stated.

### 2.4.1 Study Treatment

#### Duration of Exposure

Duration of exposure to study medication for SAF patients with a specified end date (date of last dose of study medication), i.e. for patients who permanently discontinued from study treatment or patients who completed the study:

Duration of exposure = (Date of last dose of study medication – Date of first dose of study medication + 1)

Duration of exposure to study medication for SAF patients without a specified end date:

Duration of exposure = (Date of Month 12 study cut-off date – Date of first dose of study medication + 1)

Note that duration of exposure includes periods of temporary interruption of study medication.

Duration of exposure to study regimen will be summarized in tables as follows. In addition to an overall summary of exposure duration for each study regimen, a separate summary will be made for CsA and TAC strata within a study regimen.

- Number and percentage of patients being exposed for prespecified time intervals (e.g. 1-7 days, 8-14 days, 15-30 days, 31-60 days, etc) as well as cumulative exposure.
- Summary statistics (n, mean, SD, median, Q1, Q3, minimum, maximum) for duration of exposure will also be provided.

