- 2. The Baseline visit covers the transplant period from 24 hr prior to surgery until randomization or randomization failure. Randomization must occur within 24 hr of completion of transplant surgery and post-transplant criteria for randomization (e.g. ability to take oral medication) must be met. Day 1 is the day of first dose of study drug post-randomization and for subsequent visits one week is 7 days and one month is 30 days, thus the Week 1 visit is on the seventh day from Day 1.
- 3. Viral serology includes HCV, HIV, HBV surface antigen, CMV and EBV. Measurements made within the last 6 months will be accepted, otherwise these tests should be performed within one week of randomization.
- 4. Only for females of child bearing potential, serum pregnancy tests should be carried out according to local practice. Local result must be available and negative prior to randomization.
- 5. First dose of everolimus or MPA together with applicable CNI (tacrolimus or cyclosporine) must be given immediately following randomization and within 24 hr of transplantation. Pre-transplant immunosuppression, including induction therapy and any CNI or MPA should be recorded on the Concomitant medication CRF under the immunosuppressive category.
- 6. Blood draws for everolimus, tacrolimus and cyclosporine (as applicable) trough concentrations should be performed locally as shown and additionally 5 days ± 2 days following each clinic visit in which tacrolimus, cyclosporine or everolimus doses are changed. Subject clinical management should be based on these local trough levels. At certain centers, by agreement with the sponsor, central analysis of everolimus may be performed.

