## 1 Introduction

This document presents detailed Statistical Analysis Plan (SAP) of study CRAD001A2433 entitled “A 24 month, multicenter, randomized, open-label safety and efficacy study of concentration-controlled everolimus with reduced calcineurin inhibitor vs mycophenolate with standard calcineurin inhibitor in de novo renal transplantation- Advancing renal TRANSplant eFficacy and safety Outcomes with an eveRolimus-based regiMen (TRANSFORM)”. This document covers futility, 12-month and 24-month analyses. Notable examples of analyses only to be performed at Month 12 (and not Month 24) include the non-inferiority analyses for the primary endpoint (tBPAR or eGFR(MDRD4) < 50 ml/min/1.73m^2) and the key secondary endpoint (tBPAR, graft loss or death), the superiority analysis for the primary endpoint, and the analysis for compliant patients.

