### 2.1 Data Analysis General Information

The cut-off day is defined as the latest study day before and up to which data will be used in the analysis on an individual patient level. The cut-off date for 12-month analysis will be the day of Month 12 Visit (specifically, Date of Discontinuation/Study Phase Completion as recorded on the Month 12 Disposition eCRF) + 2 Weeks, but no later than Day 450 (upper limit of Month 12 analysis window). For the 24-month analysis, there will be no cut-off day. All data in the clinical database will be used for the analyses.

Data listings will include all data collected up to the cut-off date for the 12-month analysis, or all data recorded in the database for the 24-month analysis.

For summary tables and figures, the following rules will be applied unless otherwise indicated:

- Categorical data will be summarized by frequencies and percentages. Continuous data will be summarized by mean, median, standard deviation, minimum and maximum and the number of non-missing data points.
- All AE/Infection, notable events, CMV information, EBV information and other events of interest will be summarized based on all collected events with onset on or after the first day of study medication up to the cut-off date or seven days after last dose of study medication. For SAE/infection and death, all events will be summarized.
- All lab or vital sign tables will include data up to the cut-off date or two days after last dose of study medication (on-treatment analysis);

- Efficacy and renal function analyses will be primarily based on all available data including those after study medication discontinuation; as a sensitivity analysis they will include only data up to two days after last dose of study medication (on-treatment analysis). Patients will be censored for the time to event analyses if they do not have an event. For on-treatment analysis, the censoring day is two days after discontinuation of study medication or the last contact day, whichever is earlier; for analysis regardless of on-treatment or off-treatment, the censoring day is the last contact day.
- For post-baseline continuous values, for a given patient, if multiple numeric measurements for a given variable are reported within the same visit window (see the definition for visit windows in [Section 4.1](#)), the following rule will be applied:

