**Table 4-1 Visit Windows**

Re-aligned Visit	Visit window	Relative to randomization date		
		Start day of Visit window	Midpoint	End day of Visit window
1	Screening/Baseline	Inform Consent		randomization
2	Day 4	1 (post-randomization)	4	5
3	Week 1	6	7	10
4	Week 2	11	14	21
5	Week 4	22	28	44
6	Month 2	45	60	90
7	Month 4	91	120	150
8	Month 6	151	180	225
9	Month 9	226	270	315
10	Month 12	316	360	450
11	Month 18	451	540	630
12	Month 24	631	720	810

Re-aligned Visit	Visit window	Relative to randomization date		
		Start day of Visit window	Midpoint	End day of Visit window
13	Month 12 Treatment Endpoint (TEP)	1		450
14	Month 12 Study Endpoint (SEP)	1		450
15	Month 24 TEP	1		810
16	Month 24 SEP	1		810

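### The SAP's exposure rule for patients without a last-dose date stops at the Month 12 cut-off and has no 24-month counterpart; at Month 24 it should reach few patients and affects only descriptive tables

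*SAP*

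**What the plan says.** SAP 2.4.1 (Duration of Exposure) has two formulas. The first counts from first to last dose and applies where there is a specified end date, which the SAP explains as "for patients who permanently discontinued from study treatment or patients who completed the study". The second applies to everyone else: "Duration of exposure = (Date of Month 12 study cut-off date – Date of first dose of study medication + 1").

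SAP 2.1 builds the Month 12 cut-off from each patient's own completion or discontinuation date, "as recorded on the Month 12 Disposition eCRF) + 2 Weeks, but no later than Day 450". It then says of the later analysis: "For the 24-month analysis, there will be no cut-off day". The SAP's scope is stated in its Introduction: "This document covers futility, 12-month and 24-month analyses". Exposure is not among the examples given there of analyses done only at Month 12.

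SAP 2.1.1.3 defines separate last contact days for the 12-month and 24-month analyses, but the exposure rule uses neither.

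**The concern.** At the 12-month analysis the second formula makes sense: many patients are still on drug, have no stop date, and must be counted to some date. At the 24-month analysis the same sentence, followed as written, discards all treatment time after the Month 12 cut-off for any patient whose stop date is missing, even one with dosing recorded at Month 18 or Month 24.

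The surrounding text suggests an oversight. SAP 4.2.4.3 also has a rule tied to the Month 12 cut-off and expressly confines it to the Month 12 analysis. The CNI-switching summary in SAP 2.4.1 asks for Month 12 to 24 and cumulative results, so the section is meant to serve both analyses.

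At stake are the exposure summaries, overall and by CNI, which give the background for reading the 24-month safety results. An affected patient would also be placed in the wrong interval of the exposure table. A programmer must either follow the text and truncate, or invent a rule that the SAP does not contain.

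**Working it through.** **Inputs**

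- Month length: "one month is 30 days" (Protocol Table 6-1, note 2).
- Month 12 window start, midpoint and end: "Month 12 316 360 450" (SAP Table 4-1).
- Month 24 window start, midpoint and end: "Month 24 631 720 810" (same table).
- Month 12 cut-off: Month 12 date + 14 days, capped at Day 450 (SAP 2.1).
- First dose: taken as Day 1, because Protocol Table 6-1 (note 5) requires it immediately after randomization.

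**The plan's own figures.** 12 × 30 = 360 and 24 × 30 = 720. Both match the midpoints in Table 4-1.

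**Exposure credited by the second formula.** For a Month 12 visit on Day V, exposure = min(V + 14, 450) − 1 + 1.

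| Month 12 visit | Cut-off | Days credited |
|---|---|---|
| Day 316 (window start) | Day 330 | 330 |
| Day 360 (nominal) | Day 374 | 374 |
| Day 436 or later | Day 450 (cap) | 450 |

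**Exposure if actually treated to the Month 24 visit.** 631, 720 and 810 days at the start, midpoint and end of the window.

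**Shortfall per affected patient, nominal days**

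- Treated to Month 24: 720 − 374 = 346 days, and 346/720 = 48%.
- Treated to Month 18 (Day 540): 540 − 374 = 166 days, and 166/540 = 31%.

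**Cases where these figures do not apply**

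- A patient with no stop date who left the study before Month 12 is cut at discontinuation + 14 days. For someone leaving on Day 180 (the Month 6 midpoint) that is Day 194, so there is no large loss.
- A patient who stopped drug on Day 180, stayed in the study to Month 12 on standard of care, and has a missing stop date is credited 374 days instead of 180. This over-credits 374 − 180 = 194 days.

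**Effect on an arm mean.** The documents do not give the share f of patients with an open or missing record, so f is an assumption. The fall in the mean is f × 346 if those patients were treated to Month 24, or f × 166 if to Month 18.

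| Assumed f | Treated to Month 24 | Treated to Month 18 |
|---|---|---|
| 1% | 3.5 days | 1.7 days |
| 5% | 17.3 days | 8.3 days |
| 10% | 34.6 days | 16.6 days |

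**The case against.** The strongest reply is that the second formula has almost no one left to act on at Month 24. The final analysis waits until the last active subject has had the Month 24 visit (Protocol 5.5.11). By then every patient has discontinued or completed, and the SAP assigns both groups to the first formula. Protocol 6.3 requires stop dates for these drugs. Protocol 5.5.9 uses the dosage records to capture permanent discontinuation, with loss to follow-up, death and graft loss among the listed reasons. An open record would be a data gap and not a planned state. This stands, and it makes the reach narrow.

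It can also be said that the formula's reference to a Month 12 cut-off shows it was meant for the 12-month analysis, since SAP 2.1 has the 24-month analysis use all data in the database. That is probably the intent. But confining the rule by inference still leaves the remaining patients with no rule at Month 24.

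A reader might infer more than the documents support:

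- **That a large part of an arm would be truncated because completers stay on the drug after Month 24.** If half an arm were affected, the mean would fall by 0.50 × 346 = 173 days. Protocol 5.5.11 says only that patients completing 24 months on treatment may be eligible for a separate observational study. It does not provide for continued study drug, and the SAP places completers under the first formula.
- **That every patient without a stop date gets about 374 days, or that the error always understates exposure.** The cut-off follows each patient's own date, and the error can run either way, as shown above.
- **That 24-month safety comparisons or efficacy tests are distorted.** SAP 2.4 calls these analyses descriptive. SAP 2.8 reports adverse events as incidences and relative risks, with no exposure-adjusted rate. The primary and key secondary tests do not use exposure duration.

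**Conclusion.** The point holds as a minor error in a stated rule. SAP 2.4.1 applies a Month 12 end date without limiting it to the 12-month analysis and offers nothing for the 24-month analysis that the same document governs.

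For a patient on drug after Month 12 whose last-dose date is missing or whose record is open, the nominal loss is up to 346 days (374 credited against 720). The credited figure can lie anywhere from 330 to 450, and the true figure at Month 24 anywhere from 631 to 810. These figures assume first dose on Day 1 and a Month 12 visit within its window. The number of such patients is unknown and expected to be small, so any effect on an arm mean rests on an assumed share. Nothing beyond the descriptive exposure tables changes.

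**What to change.** In SAP 2.4.1:

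1. Limit the Month 12 cut-off formula to the 12-month analysis.
2. For the 24-month analysis, where no last-dose date is specified, end exposure at the last date with evidence of study-drug dosing in the dosage administration record, and no later than the 24-month last contact day in SAP 2.1.1.3. Last contact or study completion alone would not do, because patients who stop the regimen are expected to remain in the study to Month 24 and their off-drug time would be counted as exposure.
3. Report the number of patients handled this way in each arm, so that the reader can see whether the rule matters and whether it falls unevenly.

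The cost is a sentence or two in the SAP, a small change to the exposure derivation and one count per arm in the table. No new data are needed.

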### Average Daily Doses and Body Weight-Adjusted Average Daily Doses

Average daily doses and body weight-adjusted average daily doses (for CsA and TAC only) by visit window and treatment group will also be calculated. In calculating average daily doses, zero doses will be used for periods of temporary interruption of study medication, regardless of whether this was due to safety reasons or non-compliance.

### Dose Changes and Interruptions

The number and percentage of patients with dose interruptions/adjustments will be summarized by reason for change and by the number of adjustments (any, one, two, three, more than three).

### Switching CNIs

The number and percentage of patients of remaining on their initial CNI or switching CNI at least once during the study will be summarized for each study CNI-specific study regimen. This will be provided for each study period (up to Month 12, Month 12 to 24, and cumulatively).

### Trough Levels of Study Drugs

Everolimus, cyclosporine and tacrolimus trough levels (in ng/mL) will be summarized at each visit window using descriptive statistics, and the incidence rates of patients below, within or above the trough level target ranges at each visit will be presented for patients on treatment at that visit. The target ranges for CsA and TAC trough levels are provided in [Table 2-1](#). The target range for everolimus trough levels is 3-8 ng/mL throughout the study.

Box plots of everolimus, cyclosporine and tacrolimus trough levels will be presented by visit for each treatment group. The target trough level ranges will be shown in the plots.

**Table 2-2 CNI trough level target ranges**

Study Visit	Tacrolimus target ranges		Cyclosporine target ranges	
	EVR arm	MPA arm	EVR arm	MPA arm
Day 1 ≤ Month 2	4-7 ng/mL	8-12 ng/mL	100-150 ng/mL	200-300 ng/mL
Month 3 ≤ Month 6	2-5 ng/mL	6-10 ng/mL	50-100 ng/mL	150-200 ng/mL
Month 7 ≤ Month 24	2-4 ng/mL	5-8 ng/mL	25-50 ng/mL	100-200 ng/mL

## 2.4.2 Compliance

### 2.4.2.1 Compliance for MPA

For each day, a patient is compliant to MPA as long as this patient takes MPA (non-compliant when MPA was off). If a patient is compliant for at least 70% of days on study, then this is a compliant patient.

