2.2 Secondary objectives

Key Secondary Objectives

- To evaluate everolimus with reduced exposure CNI compared to MPA plus standard exposure CNI at 12 months post-transplantation with respect to the composite efficacy failure rate of (treated biopsy proven acute rejection (tBPAR), graft loss or death).
- To evaluate the binary composite endpoint of tBPAR or eGFR < 50 mL/min/1.73m² (MDRD4) Month 12 among compliant subjects.

Other Secondary Objectives

To evaluate, by treatment group;

- The incidence of composite endpoint of tBPAR or eGFR < 50 mL/min/1.73m² (MDRD4) at Month 24.
- The incidence of composite endpoint of tBPAR (excluding Banff grade 1A acute rejections) or eGFR < 50 mL/min/1.73m² (MDRD4) at Month 24.
- The incidence of composite endpoint of tBPAR or eGFR < 50 mL/min/1.73m² (MDRD4) at Month 12 by subgroup (see Section 9.4.4).

- The incidence of composite endpoint of tBPAR, graft loss or death at Month 24.
- The incidence of composite endpoint of tBPAR, graft loss, death, or loss to follow-up at Months 12 and 24.
- The incidence of composite endpoint of tBPAR, graft loss, death or eGFR < 50 mL/min/1.73m² at Months 12 and 24.
- The incidence of composite endpoint of graft loss or death at Month 12 and 24.
- The incidence of individual endpoints of death, graft loss, tBPAR, BPAR, tAR, AR and humoral rejection at Months 12 and 24.
- The incidence of tBPAR by severity and time to event.
- The incidence of tBPAR excluding Banff 1A grade acute rejections
- The incidence of transplant recipients with eGFR < 50 mL/min/1.73m² at Months 12 and 24.
- Renal allograft function and change in renal allograft function from Month 1 (eGFR) at Months 12 and 24.
- The evolution of renal function, as eGFR, over time by slope analysis.
- Renal function by Cystatin C-based and other alternate formulae (e.g. CKD-EPI).
- The incidence of adverse events, serious adverse events and adverse events leading to study regimen discontinuation.
- The incidence of CMV and BKV, new onset diabetes mellitus, chronic kidney disease with associated proteinuria and CNI associated adverse events.
- Urinary protein and albumin excretion by treatment estimated by urinary protein/creatinine and urinary albumin/creatinine ratios.
- The incidence of major cardiovascular events.
- The incidence of malignancies.

3 Investigational plan

[figure not shown]

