## 2.2 Analysis Sets

The **full analysis set** (FAS) consists of all randomized and transplanted patients. Patients randomized but not transplanted will be excluded from the FAS. Patients who are mis-randomized due to documented (IVRS) administrative error (eligibility criteria) and have no study drug received are excluded from the FAS. Following the intention-to-treat (ITT) principle, patients will be analyzed according to their randomized treatment assignment and according to the actual stratum they initially belong to.

The **compliance set** (CS) consists of all patients in the FAS who are compliant for both CNI and investigational drug (EVR/MPA). Compliance is defined in [Section 2.4.2](#).

The **per-protocol set** (PPS) consists of all patients in the FAS who complete the study without any major deviations from protocol procedures. Major deviations include:

- Patient received multiple solid organ or tissue transplants (PD ID: EXCL04)
- Renal cold ischemia time > 30 hr (PD ID: INCL04)
- Patient received kidney from a non-heart beating donor (PD ID: INCL06)
- Patient Stratified incorrectly (PD ID: TRT08)
- Patient randomized but did not receive study drug (EVR or MPA) (PD ID: TRT01)
- Patient received treatment other than what they were randomized to (PD ID: TRT07)
- Induction agent other than basiliximab or rATG used (PD ID: TRT05)
- Patient did not receive any basiliximab or rATG for induction use (PD ID: TRT06)
- Prohibited Concomitant Medication used (PD ID: COMD03)
- Prednisone or equivalent was not used during the study (PD ID: TRT14)

The **safety set (SAF)** consists of all patients who received at least one dose of study drug. Patients will be analyzed according to their actual treatment regimen and according to the actual stratum they initially belong to. All safety analyses will be performed on the SAF.

Patients who did not sign the study main informed consent form will be excluded from any analysis sets (FAS, PPS, CS, and SAF). If a patient was mis-randomized due to documented (IVRS) administrative error (eligibility criteria), but received study drug, this patient will belong to both FAS and SAF. [Table 2-1](#) illustrates the selection of patients for the FAS and SAF.

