### 2.4.2.2 Compliance for CNI/EVR:

To evaluate patient compliance for CNI/EVR, CNI/EVR trough levels will be imputed (see [Section 4.2.2](#) for details) for each day from the date of the first dose of the respective study drug (CNI/EVR) to the maximum study drug on-treatment date, which is defined as the minimum of (the date of the last study drug dose plus two days or the last contact day). For each day, patient compliance will be assessed by comparing the imputed trough level with the corresponding

target trough level range. If a patient was compliant for at least 70% of days on study, then this is a compliant patient.

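### The compliant-set analysis filters everolimus on trough exposure but MPA only on intake, so the second-drug rule selects the two arms differently

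*SAP*

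**What the plan says.** SAP 2.2 defines the compliance set: it "consists of all patients in the FAS who are compliant for both CNI and investigational drug (EVR/MPA"). SAP 2.4.2 gives the daily rules.

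- **CNI and everolimus (SAP 2.4.2.2):** "For each day, patient compliance will be assessed by comparing the imputed trough level with the corresponding" target range. The everolimus range is fixed in SAP 2.4.1: "The target range for everolimus trough levels is 3-8 ng/mL throughout the study". The CNI ranges are arm-specific (SAP Table 2-2). Troughs are imputed from first dose up to "the minimum of (the date of the last study drug dose plus two days or the last contact day").
- **MPA (SAP 2.4.2.1):** "a patient is compliant to MPA as long as this patient takes MPA (non-compliant when MPA was off"). No dose or level condition is attached, and no assessment window is given.
- **Patient level:** the threshold is the same in both rules: "If a patient was compliant for at least 70% of days on study, then this is a compliant patient".

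SAP 2.5.4.1 repeats the whole of Section 2.5.2 on this set, that is, non-inferiority and superiority for the primary endpoint. SAP 2.7.2.1 uses the set again at Month 24, although SAP Section 1 lists the compliant-patient analysis among those done only at Month 12. Protocol 2.2 places the endpoint at "Month 12 among compliant subjects" under the key secondary objectives. Protocol 9.4.4 and SAP 2.5.4 treat the analysis as supportive.

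**The concern.** An everolimus patient must pass two exposure tests. An MPA patient must pass one exposure test (CNI) and one intake test. A patient who takes every everolimus dose but has troughs just under 3 ng/mL on more than 30% of days is excluded. A patient on a long-term reduced MPA dose is retained.

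The extra test is not neutral. Protocol 1.1 reports that everolimus exposure above 3 ng/mL was adequate for reducing tBPAR risk. It adds that the lowest rates of renal dysfunction were generally seen at 3-8 ng/mL together with low cyclosporine levels, and that troughs above 8 ng/mL were associated with proteinuria. Those outcomes bear on both components of the primary endpoint. Trough is measured after randomization and reflects tolerability, interactions and clinical course as well as adherence. Conditioning on it in one arm only can create a difference between arms with no treatment effect, or hide a real one. The result would then be read beside a 10-point margin and a superiority bound of zero.

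**Working it through.** **1. The rules side by side**

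| | Everolimus arm | MPA arm |
|---|---|---|
| CNI | trough in arm's range, ≥70% of days | trough in arm's range, ≥70% of days |
| Second drug | trough in 3-8 ng/mL, ≥70% of days | taken, ≥70% of days |
| Dose or level condition on second drug | yes | none |

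**2. The plan's own figures.** Protocol Table 9-1 covers the FAS and PPS only. Its non-inferiority column reproduces with Φ(0.10/√(2·0.5·0.5/n) − 1.96). For n = 816: 0.10/0.02475 = 4.04, and Φ(2.08) = 98.1% (stated 98). For n = 1020, 714, 653 and 571 the results are 99.5, 96.6, 95.1 and 92.2% (stated >99, 97, 95, 92). No size or power is given for the compliance set, so its consequences can only be illustrated.

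**3. Retention.** All pass rates here are assumptions. With CNI passed by 60% in each arm, independently of the second drug, the number kept is 1020 × 0.60 × second-drug pass rate.
- Everolimus pass rate 50 / 70 / 90%: 306 / 428 / 551 kept.
- MPA pass rate 85 / 95%: 520 / 581 kept.

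Most combinations keep fewer everolimus patients, but 90% against 85% keeps more (551 against 520).

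**4. Simple shift.** Suppose excluded patients have an event rate g points above included ones in both arms, and a share s is excluded. The included rate is then the overall rate minus g·s. With equal overall rates, the artefact in everolimus minus MPA is −g(s_EVR − s_MPA).
- s = 25% and 10%, g = 15: −15 × 0.15 = −2.25 points. With g = 10: −1.5 points.
- s = 10% and 15%, g = 15: −15 × (−0.05) = +0.75 points, now against everolimus.

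**5. Simulation.** There were 1,000,000 patients per arm, a 50% event rate and no treatment effect. Each compliance score had the stated latent correlation with a good outcome. MPA intake was passed by 95%, and the CNI test by 40, 60 or 80%, equal in both arms. Everolimus minus MPA in the compliant set, in points:

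| Everolimus pass rate | Correlation 0.2 | Correlation 0.4 |
|---|---|---|
| 50% | −5.3 to −5.4 | −9.0 to −10.5 |
| 70% | −2.9 to −3.0 | −5.1 to −6.0 |
| 90% | −0.6 to −0.8 | −1.0 to −1.3 |

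At correlation 0 every difference is within 0.3 points of zero. The uniform sign follows from setting the MPA pass rate above every everolimus pass rate.

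**6. Features that may pull the other way.** Both rules count days on study without defining the denominator. If the everolimus/CNI denominator is the imputation window, a patient who stops both at Day 180 with all troughs in range scores 100%. A patient who stops MPA at Day 180 of 360 scores 180/360 = 50% and fails, because 0.70 × 360 = 252 days are needed. SAP 4.2.2 also gives every day in the window a trough and states no exception for temporary interruptions, whereas an MPA day off counts against the patient.

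**7. The CNI test.** It applies to both arms, but to different ranges.
- Tacrolimus widths over the three periods: 3, 3, 2 ng/mL (everolimus arm) against 4, 4, 3 (MPA arm).
- Cyclosporine widths: 50, 50, 25 ng/mL against 100, 50, 100.
- As ratios of upper to lower limit, the everolimus-arm ranges are as wide or wider. For tacrolimus these are 7/4 = 1.75, 5/2 = 2.5 and 4/2 = 2, against 12/8 = 1.5, 10/6 = 1.67 and 8/5 = 1.6.

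Which arm faces the stricter CNI test therefore cannot be read off the table.

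**The case against.** The best defence is that each regimen is judged against its own instructions. Everolimus is concentration-controlled; MPA is given by stated dose. Protocol Table 6-1 schedules no MPA trough and no MPA target exists, so a matching trough test was not available. Protocol 3.6 itself describes compliance in terms of CNI and everolimus target levels. Protocol 5.5.4 and Appendix 3 provide for reduced MPA doses, so counting them as compliant fits the plan. This stands as a reason to keep the trough-based set. It does not make the retained arms comparable, and a common intake rule was available.

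Three stronger readings are tempting but not supported:
- **That the MPA arm is effectively unfiltered.** It must also have in-range CNI troughs and take MPA on at least 70% of days. MPA intake is itself response-related, since Appendix 3 mandates interruption for low platelets or WBC.
- **That the rule favours everolimus.** Steps 4 and 6 show that the sign depends on unknown pass rates and on an undefined denominator.
- **That a confirmatory claim is compromised.** Despite the listing in Protocol 2.2, the analysis is outside the three-step hierarchy in Protocol 9.4.2 and SAP 2.5.2. SAP 2.6.1 names a different, single key secondary endpoint.

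It is also true that any compliant set is non-randomized, so a common rule reduces the problem without removing it.

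**Conclusion.** The arms are selected by different second-drug rules, and only the everolimus arm passes a second exposure filter, one that the protocol itself ties to rejection and renal function. The compliant-set results at Month 12, and at Month 24 if performed, are therefore not a like-for-like comparison. The illustrations range from about zero to several points, which matters against a 10-point margin and the 5- to 8-point differences considered in Table 9-1. They rest on assumed pass rates, an assumed link between compliance and outcome, and equal CNI pass rates. The documents fix neither the net direction nor the size. The FAS primary analysis, the test hierarchy and type I error control are unaffected. The change is worth making for interpretation of a supportive analysis.

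**What to change.** - Keep the present trough-based set and label it as the exposure-attainment analysis.
- Repeat the Section 2.5.2 analysis on a like-for-like set: everolimus and MPA each taken on at least 70% of days, with the CNI trough rule in both arms.
- Use one denominator for all drugs: days from first dose to the earliest of tBPAR, graft loss, death, last contact or the Month 12 cut-off, with days off drug counted as non-compliant. Ending the count at the event matters. A fixed Day 1 to Month 12 denominator would exclude patients who stop drug because they died or lost the graft, and so would select on outcome.
- Report the number retained per arm for both sets.
- Describe both results as supportive and non-randomized, and note that the CNI ranges still differ by arm.
- Reconcile SAP Section 1 with SAP 2.7.2.1 on whether the compliant set is analysed at Month 24.

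The cost is SAP wording, one extra derivation and one extra set of outputs. No new data are needed, because dose records for both drugs are already collected.
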